	
 Self-reported activities (e.g., coughing, sports, sleeping) as collected by the participant app Self-reported satisfaction to the study, collected via end of study questionnaire 
Covariates will be collected from patient records (status at the time of Day 0, closest record prior to):
 
 Demographics, Body mass index, Smoking status Relevant medical history, comorbidities, current medication including COPD treatment at baseline Date of diagnosis of COPD and COPD severity (GOLD stage) Number of moderate or severe exacerbations prior to baseline visit (at Day 0, moderate/severe exacerbation visit and End of study visit): Current body plethysmography parameters Current (capillary) pO₂, O₂ saturation and pCO₂ 
Several biomarkers at the time of baseline depending on availability

Data Sources	
The data source used for this study will consist of patients charts from 11 sites (mainly pulmonology private practices) in Germany as well as from a device, which will get handed out to the participant.
 
The data informing this study will be extracted from patient medical records using eCRF directly in an electronic data capture system. In addition, a patient reported outcomes (PRO) questionnaire (COPD assessment tool [CAT], filled in by the participant electronically), and a wearable device (adhesive patch device with sensors) will be used for data collection.

Study Size	
Sample size required to show a sensitivity of ≥ 0.85 for a model predicting moderate to severe COPD exacerbations was estimated to be 67 participants including a drop-out rate of 10%. The study will also observe 10 participants in the calibration cohort for 2 weeks. The number of participants for this cohort is chosen on an exploratory basis.

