Specifically, this study aims at predicting 2 target outcomes: acute exacerbations of COPD (AECOPDs) as defined by the GOLD initiative, and the CAT score as a proxy for patients' disease status. The start of an exacerbation within a patient, regardless of how many exacerbations the patient may have experienced before, will be predicted based on sensor data preceding the

exacerbation, and using basic covariates as well. For type of exacerbations, the severe and moderate exacerbations are considered as our main target as these are linked to the need of urgent medical intervention and will predict those as a group, but also separately (distinguish by type), if possible. Mild exacerbations, the relevance of which is currently a subject of investigation in the field, will also be explored.

For the CAT score, the aim is to predict the total score (max = 40) from the sensor data, and changes in the CAT score of ≥ 2 based on the MCID. With this approach, it is aimed to use the model built on sensor data as an objective means to reflect patients' disease status. While for the prediction of exacerbations the aim is to predict them as early as possible, i.e. days before an exacerbation, for the CAT/disease status prediction the aim is to reflect the daily status.

CCI

This study is exploratory in nature and any predictive models will need to be validated in future studies. A future remote patient monitoring (RPM) solution for patients with COPD built on these models will have 2 prime utilities: First, ameliorating or preventing exacerbations and their negative sequelae by early treatment intervention and second, to provide physicians and patients with a highly granular and precise view on the current disease status and past changes. Such information can be used by the treating physician to optimize therapeutic regimens and by the patients to accompany and optimize lifestyle changes. By using a multimodal sensor approach we intend to increase the accuracy of our predictive models beyond what has been described in the literature and thereby increase their clinical utility.

8 Research Question and Objectives

The aim of the study is to investigate the correlation of real-world sensor-derived biometric data obtained via a wearable device with clinical parameters and PROs for monitoring disease activity and predicting exacerbations for patients with COPD.

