9.7.1.2 Missing Data

For variables obtained only at the baseline visit, missing values will not be replaced.

For the self-reported satisfaction questionnaire items, collected at the end of study visit, missing values will not be replaced. For variables measured daily during the observation period such as sensor-generated data, CAT score, and labelling information, missing data will not be imputed for all descriptive statistical analyses performed. The CAT score and derived sensor variables may be imputed for the purpose of building machine learning models if needed to avoid loss of instances

using a suitable imputation method (e.g. LOCF, forward filling, multiple imputation [MI]). Sensitivity analyses will be conducted to assess the impact of imputation.

For variables with values collected at baseline, at the exacerbation visit and at end of study visit, missing values will not be imputed for all descriptive statistical analyses. Lung function parameters and laboratory values may be imputed for the purpose of building machine learning models if needed to avoid loss of instances by LOCF method if the last (previous) available value is recorded within 2 weeks before the date of the visit of interest. In cases where no value for a variable is available for a participant, imputation strategies across instances may be used (e.g. median imputation or iterative imputation methods). Sensitivity analyses will be conducted to assess the impact of imputation.

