9.7.2.1 Primary Objectives

Primary objective 1): To describe the distribution of sensor collected data on physical activity, heart rate, heart rate variability, temperature, respiration rate, cough frequency, and sleep pattern, by severity of COPD exacerbations.

This analysis will be performed on the COPD participants set.

- Sensor collected data on physical activity, heart rate, heart rate variability, temperature, respiration rate, cough frequency, sleep pattern, at baseline (Day 0), in the period Day 8 to Day 14, and shortly prior (14 days prior to, 7 days prior) to, during an exacerbation and after an exacerbation (8 to 14 days after, 2 weeks after, 3 weeks after, up to 4 weeks after an exacerbation) will be reported as mean (SD) and/or median (Interquartile Range) for continuous variables and counts and frequency (%) for categorical variables. The analysis will be done on the group of severe or moderate exacerbations and on exacerbations by type.

Primary objective 2): To predict moderate or severe COPD exacerbations by building a statistical model employing sensor-derived data and demographic and medical covariates.

This objective aims at predicting the occurrence of a severe or moderate exacerbation, in other words, predicting an event out of the combined group of severe and moderate exacerbations. It is desirable to predict an AECOPD as early as possible, therefore dependency of model metrics on the time period before exacerbation will be explored.

As input to the model a number of algorithms (e.g. self-learning algorithms) for obtaining derived parameters such as cough frequency, physical activities and sleep pattern, heart rate variability, temperature, respiration pattern, cough frequency, or sleep pattern will be developed first using the labeling of activities dataset obtained via the app. Said derived features will help to understand the importance of different raw data patterns, so that explanatory models can be built on top of the machine learning algorithms (Molnar 2022), as a way to support rationalization for physicians and regulatory organizations.

Different machine learning algorithms (e.g. gradient boosting, SVMs, K-nn) will be evaluated, and their performance will be assessed by estimating their accuracy, specificity, sensitivity, and area under ROC metrics.

This analysis will be performed on the COPD participants set.

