2	To predict moderate or severe COPD exacerbations by building a statistical model employing sensor-derived data and demographic and medical covariates.	Severe/moderate COPD exacerbations (requiring a physician's intervention, emergency room visit or hospitalization) during the observation period.	
COPD exacerbation from the physician charts (for the severe/moderate exacerbation):
 
 - Occurrence (Yes/No) of COPD exacerbation - Severity of COPD exacerbation (moderate, severe) 
Sensor data (Vivalink wearable device) collected daily:
 
 - Physical activity including stair climbing (derived parameter) - Heart rate as beats per minute [daily average] (derived parameter) - Resting heart rate [daily average] (derived parameter) - Heart rate variability [daily average] (derived parameter) - Temperature [daily average, minimum -maximum values] - Respiration rate (breath per minute) [daily average] (derived parameter) - Ratio of in- vs expiration time [daily average min-max] (derived parameter) - Cough frequency (derived parameter) - Sleep pattern (derived parameter) 
Self-reported activities (e.g., coughing, sports, sleeping) as collected by the participant app:
 
 - Coughing - coughing with sputum production - spray use, non-scheduled spray use - eating, going to bed, waking up - walking, climbing stairs - physical exercise 
Other covariates (at Day 0) from the physician chart:
 
 - Demographics data at baseline: (sex, age, height, and weight, race and ethnicity) - Body mass index will be calculated based on height and weight - Smoking status (current, ex-, non-smoker) - Medical history at baseline - Date of diagnosis of COPD

Number of objective	Objective	Outcome definition	Variables and Sources

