			
 - Number of moderate or severe exacerbations prior to baseline visit (preceding 36 months, in case available) - Comorbidities at baseline - Current medication including COPD treatment at baseline - COPD severity (GOLD stage) 
Other covariates (Lung Function and Laboratory variables at Day 0, moderate/severe exacerbation visit and End of study visit) from the physician chart:
 
 - Body plethysmography parameters: FEV1 [L], FVC [L], FEV1/FVC, TLC [L] (total lung capacity), RV [L] (residual volume), FRCpleth [L] (functional reserve capacity), IC [L] (inspiratory capacity), Raw [kPa s L-1] (=ratio of sRaw to FRCpleth; airway resistance), sRaw [kPa s] (specific airway resistance), VT [L] (mean tidal volume), ERV [L] (expiratory reserve volume), IRV [L] (inspiratory reserve volume). - Blood gas analysis: (capillary) pO2 [mmHg], O2 [%] saturation and pCO2 [mmHg] - Serum CRP [mg/l] and serum procalcitonin levels [ng/ml] - Blood count (CBC with differential); only values that are available with routine blood counts: Hb [g/dL], Hct [%], Erythrocyte count [$10^6/\mu\text{L}$], MCV [fL], MCH [pg], MCHC [g/dL], Reticulocytes [$\times 10^3/\mu\text{L}$] [% (of erythrocytes)], RDW [], platelet count [$10^3/\mu\text{L}$], WBC count [$\times 10^3/\mu\text{L}$], Lymphocytes [$\times 10^3/\mu\text{L}$] [%], Monocytes [$\times 10^3/\mu\text{L}$] [%], Neutrophils [$\times 10^3/\mu\text{L}$] [%], Eosinophils [$\times 10^3/\mu\text{L}$] [%], Basophils [$\times 10^3/\mu\text{L}$] [%]

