## 2.3 OUTCOME DEFINITIONS

### 2.3.1 Outcomes for primary objectives

The primary outcomes are based on COPD exacerbations. Exacerbations are classified as

- 1) mild if they are treated with short-acting bronchodilators only,
- 2) moderate if they are treated additionally with antibiotics or oral corticosteroids, or
- 3) severe if the patient visits the emergency room or requires hospitalization because of an exacerbation.

The occurrence of exacerbations during the observation period is measured as follows.:

- For moderate/severe exacerbation requiring a physician's intervention, exacerbation details will be recorded via eCRF by the clinical site. Severity, onset and duration will be derived according to the definition above from the documented COPD medication associated with the patients' exacerbation visit. The definition details for COPD medication and ATC codes will be finalized during the planned Data review meeting prior to the final analysis.
- For mild exacerbations: self-reported; treated by the participant without intervention by a physician will be documented in the patient application labeling section (days with added treatment: short-acting bronchodilators only). The start date and end date of addition of short-acting bronchodilators can thus be retrieved from the patient application. The documented use of additional medication (Bedarfsmedikament) will be considered as a mild exacerbation with the following rules for start and end days:
  - A mild exacerbation must start with at least 2 consecutive days of additional medication reported, the first day of consecutive medication will determine the start of the exacerbation.
  - If there are gaps in the additional medication reporting, a maximum of 2 days is allowed to be considered only one exacerbation. A minimum of 70% of the days must have additional medication reported. The end date of the exacerbation is the last day where both these rules are fulfilled.
- Any exacerbations that happen within 5 days will be considered as overlapping, as well as exacerbations that have an intersection in their start and end dates. Overlapping exacerbations will be considered as only one and classified as the graver one. (4)
  - If all overlapping exacerbations have the same type, the start date is the start date of the first exacerbation, and the end date of the last one.

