### 3.4.4 Handling of missing data

For variables obtained only at the baseline visit, missing values will not be replaced.

For the self-reported satisfaction questionnaire items, collected at the end of study visit, missing values will not be replaced. For variables measured daily during the observation period such as sensor-generated data, CAT score, and labelling information, missing data will not be imputed for all descriptive statistical analyses performed. The CAT score and derived sensor variables may be imputed for the purpose of building machine learning models if needed to avoid loss of instances using a suitable imputation method (e.g., LOCF, Forward filling, multiple imputation [MI], recursive imputation, median imputation). Sensitivity analyses will be conducted to assess the impact of imputation.

For variables with values collected at baseline, at the exacerbation visit and at end of study visit, missing values will not be imputed for all descriptive statistical analyses. Lung function parameters and lab values may be imputed for the purpose of building machine learning models if needed to avoid loss of instances by LOCF method if the last (previous) available value is recorded within 2 weeks before the date of the visit of interest. In cases where no value for a variable is available for a participant, imputation strategies across instances may be used (e.g., median imputation or iterative imputation methods). Sensitivity analyses will be conducted to assess the impact of imputation.

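### Objective 2 lists lung-function and laboratory values from the exacerbation visit as covariates, and no visible rule excludes the visit for the exacerbation being predicted

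*Protocol*

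**What the plan says.** Protocol 14.1.2, objective 2 row, has two groups of chart covariates. The first (demographics, smoking, history, comorbidities, medication, GOLD stage) is headed "Other covariates (at Day 0) from the physician chart". The second (plethysmography, blood gases, CRP, procalcitonin, blood count) is headed "Other covariates (Lung Function and Laboratory variables at Day 0, moderate/severe exacerbation visit and End of study visit) from the physician chart". In the objective 3 row the same lung-function and laboratory variables are tied to the baseline and study-end visits only.

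The covariate block in the Protocol abstract (section 4, Key Variables) opens with Day 0 status but then gives the three visits again: "at Day 0, moderate/severe exacerbation visit and End of study visit): Current body plethysmography parameters". Protocol 9.3 and SAP 2.1.3 give the same three time points for measurement.

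On timing relative to the event, Protocol section 7 says that the start of an exacerbation, "regardless of how many exacerbations the patient may have experienced before, will be predicted based on sensor data preceding the" exacerbation, with basic covariates added. Protocol 9.7.2.1 calls early prediction desirable and adds that "dependency of model metrics on the time period before exacerbation will be explored". SAP 3.4.2 says that the predictive modelling will consider whatever features are available. SAP 3.4.5.2 names algorithms, metrics and feature selection, but gives no rule on the date of a feature.

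**The concern.** CRP, procalcitonin, blood gases and lung function at an exacerbation visit are measured because the exacerbation has occurred. If they enter the model as predictors of that same exacerbation, the model can recognise an event already under way instead of forecasting it. That part of the performance could not be reproduced in the intended use, which is warning days ahead. Sensitivity, specificity and AUC for this model are the reported result of a primary objective, so an upward bias in them goes to the main finding.

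**Working it through.** The plan's own figures first; this point disputes none of them.

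- Events (Protocol 9.5): true sensitivity 0.85, lower 95% limit at least 0.50 with probability 0.95. With an exact one-sided limit, n = 18 needs at least 13 correct, and P(X ≥ 13 | 18, 0.85) = 0.958; n = 17 gives 0.901. So 18 reproduces.
- Participants: 60 × 0.5 = 30 expected events; Poisson P(X ≥ 18 | 30) = 0.993. So 60 reproduces.
- Drop-out: 60 / 0.9 = 66.7, rounded up to 67.

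The rest is a reading of the text.

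1. *Does the mapping table assign time points by objective?* Yes. The first covariate group for objective 2 is limited to Day 0, the second has three visits, and the objective 3 row drops the exacerbation visit for the same variables. Read literally, the exacerbation visit is assigned to objective 2.

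2. *Does any visible text remove the index-visit value?*
   - Protocol section 7 attaches the requirement to precede the exacerbation to sensor data; the basic covariates carry no date limit there.
   - Protocol 9.7.2.1 explores lead time but sets no covariate cut-off.
   - The 2-week rule in Protocol 9.5 and SAP 2.3.1 governs which days may be sampled as non-events, not the dates of covariates.
   - The imputation rule ("Lung function parameters and laboratory values may be imputed for the purpose of building machine learning models if needed to avoid loss of instances") fills gaps "by LOCF method if the last (previous) available value is recorded within 2 weeks before the date of the visit of interest". It looks back from a visit to fill a missing value and leaves a value measured at that visit in place.
   - SAP 3.4.2 and 3.4.5.2 add no restriction.

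3. *Why this would leak.* Under SAP 2.3.1 the outcome is occurrence at the onset date. Non-event days fall outside exacerbation periods and avoid 2 weeks before onset and 2 weeks after the end. A value measured during an exacerbation can therefore be current for an event instance, but is at least 2 weeks away from any non-event instance. Exacerbation-visit values also exist only for participants who had an event, so their mere presence can carry the outcome.

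4. *Would the planned validation catch it?* No. The internal cross-validation in SAP 3.4.5.2 uses the same features in every fold, so training and test data carry the same leak.

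5. *Would a date rule alone be enough?* Not safely. SAP 2.3.1 states: "Severity, onset and duration will be derived according to the definition above from the documented COPD medication associated with the" patient's exacerbation visit. Onset and visit dates may coincide or be ordered by how medication was recorded, so the index visit has to be excluded by name.

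6. *Size.* The documents do not give it. Any event with values recorded at its own visit is exposed, and Protocol 9.2.4 (Table 4) takes laboratory values only if clinical practice supplies them. The following is purely illustrative and rests on assumptions not in the documents. Suppose the sensors carry no signal and one leaked, normally distributed variable is shifted by d SD at the index visit and is available for every instance. Then AUC = Φ(d/√2), and sensitivity at specificity 0.85 = Φ(d − 1.036):

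| d (assumed) | AUC | Sensitivity at specificity 0.85 |
|---|---|---|
| 0 | 0.50 | 0.15 |
| 0.5 | 0.64 | 0.30 |
| 1 | 0.76 | 0.49 |
| 2 | 0.92 | 0.83 |
| 2.5 | 0.96 | 0.93 |

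This shows only that a leak could matter against the 0.85 target. It does not estimate the bias in this study.

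**The case against.** The case against is substantial.

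- *The table is an inventory.* Its column lists variables and sources and does not say which value goes with which instance. The same block recurs for objective 5, where the aim is to reflect daily status and same-time values are legitimate. This stands, and it is why the documents cannot be said to prescribe leakage.
- *The intent is prospective.* Protocol 9.3 heads its covariates as Day 0 status and puts lung function and laboratory values under a separate heading; the mixed block in the abstract may be a sub-heading lost in text extraction. The abstract's list also ends with biomarkers at baseline, and laboratory values from an exacerbation visit are hard to call basic covariates. This stands as evidence of intent, but none of it is a rule, and the objective 2 row does call the visit values covariates.
- *There are partial safeguards.* SAP 3.4.6 reruns models with variables missing in at most 20%, which might drop sparse visit values. The explanatory models in SAP 3.4.5.2 might show a model dominated by them. The Protocol says that its models need later validation. These could reveal the problem after the fact; they do not prevent it.

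Some stronger readings are tempting but not supported:

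- *That the imputation rule shows visit values are meant for the objective 2 model.* The rule serves all the machine learning models, and objective 5 alone would explain it.
- *That the rule's 2-week limit caps how long a Day 0 value may be used.* The limit is anchored to visits, not to sampled days.
- *That exposure can be sized by counting participants' first in-study events.* A later event has its own index visit and is equally exposed if values were recorded there.
- *That End of Study values are a likely leak.* No visible rule carries them back to an earlier onset; that part is a listing to correct.

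**Conclusion.** The concern holds as a missing rule, and it should be fixed before any model is built. The Protocol lists exacerbation-visit values as covariates for the model that predicts exacerbations, the SAP admits all available features, and nothing visible excludes the index visit. A reader might infer that the sponsor will use index-visit values; the documents do not say so, and redacted text could not be checked. The harm is therefore conditional: if the listing is followed literally, the performance metrics of a primary objective are biased upward by an amount that the documents do not allow anyone to estimate. The argument assumes that the visit falls within the exacerbation and that some lung-function or laboratory values are recorded there. Confidence is high that the rule is absent; whether leakage would in fact occur is not known.

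**What to change.** Add to SAP 3.4.5.2, for objective 2:

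> *Lung-function and laboratory predictors, including imputed ones, are limited to values dated before the onset date (event instances) or before the sampled day (non-event instances), less any lead time being explored, and are selected by the same rule for both. Values from the visit for the exacerbation being predicted are excluded whatever their date. End of Study values are not predictors. Values from the visit for an earlier exacerbation may be used for a later onset.*

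The last sentence keeps legitimate information, since each onset is predicted whatever the number of earlier ones. Index-visit values remain available for the descriptive tables, and End of Study values for those tables and objective 3.

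At the next protocol amendment, bring the objective 2 row of 14.1.2 and the covariate list in the abstract into line. Protocol changes have to be notified to the ethics committee and the authority (Protocol 9.10.2 and 9.10.4), so it is sensible to put the rule in the SAP first.

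The cost is a short paragraph now and two small edits later. No new data are needed, and 18, 60 and 67 stay as they are. The downside is that reported performance may be less favourable.
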